9.2. Analysis Sets

9.2.1. Intent-to-Treat Analysis Set

The intent-to-treat (ITT) analysis set will include all enrolled patients regardless of whether or not a patient took any IMP. A patient is considered enrolled according to the status reported in the database. This analysis population will be used for summarization of patient disposition.

9.2.2. Modified Intent-to-Treat Analysis Set

The modified intent-to-treat (mITT) analysis set is a subset of the ITT analysis set that will include only the patients who used the IMP at least once during the study. This analysis population will be used for endpoint analyses.

9.2.3. Safety Analysis Set

The safety analysis set will include all enrolled patients who receive at least 1 dose of the test IMP. This analysis population will be used for analysis and summarization of safety data.

9.3. Data Handling Conventions

For all variables, only the observed data from the patients will be used in the statistical analyses, that is, there is no plan to estimate (impute) missing data, unless otherwise specified in the analysis plan.

9.3.1. Handling Withdrawals and Missing Data

Missing data will not be imputed, unless otherwise specified in the statistical analysis plan.

9.4. Study Population

The cohort will consist of patients 40 years of age or older with moderate or severe CE-COPD (see Section 6.1.1) in the past 12 months.

9.4.1. Patient Disposition

Data from patients screened; patients screened but not enrolled and reason for non-enrollment; patients who are enrolled; patients enrolled but not treated; patients in the ITT, safety, and mITT analysis sets; patients who complete the study; and patients who withdraw from the study will be summarized using descriptive summary statistics (n, %). Data from patients who withdraw from the study will also be summarized by reason for withdrawal using descriptive statistics.

9.4.2. Demographic and Baseline Characteristics

Patient demographic and baseline characteristics, including medical history and prior medications and therapies, will be summarized using descriptive statistics. For continuous variables, descriptive statistics (number, mean, standard deviation, median, minimum, and maximum) will be provided. For categorical variables, patient counts and percentages will be provided. Categories for missing data will be presented if necessary. This will be based on the ITT analysis population.

9.5. Endpoint Analysis

9.5.1. Endpoints

The endpoints of the trial are the primary outcome measure (ie, CE-COPD) and the primary outcome predictor (ie, albuterol use) alone or in combination with secondary predictors (ie, other study data, including inspiratory flow, SDI, TDS, disease state at baseline, and demographics at baseline) of CE-COPD. These predictors of CE-COPD will be modeled to determine which patterns best predict the subsequent development of CE-COPD. For albuterol use, examples of correlates of CE-COPD of interest include (1) the total number of inhalations in the days preceding the peak of a CE-COPD, (2) the number of days prior to the peak of a CE-COPD when albuterol use increased, and (3) the number of albuterol uses in the 24 hours preceding a CE-COPD.

Albuterol use and inspiratory flow values are obtained from the eMDPI, SDI is obtained for a subset of patients (n=100) from an accelerometer worn on the wrist, and TDS is obtained for a subset of patients (n=100) from an accelerometer worn on the ankle. Baseline disease state and demographic information will be obtained at screening.

The following 8 surrogate measures of sleep disruption are available from the accelerometer worn on the wrist: (i) sleeptime average total time in bed, (ii) sleeptime average total sleep time, (iii) sleeptime average sleep latency time, (iv) sleeptime average wakening after sleep onset, (v) total time awake at night, (vi) longest sleeptime wake episode, (vii) daytime average minutes asleep, and (viii) longest daytime sleep episode.

The SDI for analysis in this study is the composite endpoint derived from the summation of sleeptime average sleep latency time, longest sleeptime wake episode, and total time awake at night. These 3 surrogate measures were correlated significantly with SABA rescue use (sleeptime average sleep latency time ($r=0.78$), longest sleeptime wake episode ($r=0.73$), and total time awake at night ($r=0.65$) ([Krouse et al 2008](#)).

9.5.2. Planned Method of Analysis

The mITT analysis set (Section [9.2.2](#)) will be used for all endpoint analyses. Individual listings will be presented by patient.

9.5.2.1. Endpoint Analysis

The relationship between albuterol usage and CE-COPD will be analyzed as follows, without controlling for multiplicity.

The multiple device-use-measures will be used as predictors of CE-COPD in the following stepwise selection logistic regression models to select significant predictors in a forward manner:

1. albuterol usage
2. albuterol usage + inspiratory flow values
3. albuterol usage + SDI
4. albuterol usage + TDS
5. albuterol usage + inspiratory flow values + SDI

6. albuterol usage + inspiratory flow values + TDS

The selection of covariates will be performed at the 0.2 level.

Demographic variables and disease state information collected at study enrollment will also be considered as predictors. Because the device-use-measures will be collected continuously over time, these measures could be used to derive many potential predictors of risk. For example, with respect to albuterol use, a subject using the inhaler 3 times in the span of a 2-day or 3-day period could be a strong predictor of a CE-COPD, but a better marker for risk might be 10 times in the span of a week. There are no prior robust data to inform these decisions; 1 possible benefit of this work will be to examine the relationship between multiple functional forms for the device-use-measures to determine which forms have predictive power.

Furthermore, the effect of including interaction terms in the model (ie, testing the assumption of additivity of predictors on the log odds scale) will also be studied. Pair-wise interactions will be assessed at the 0.01 significance level to avoid weak interaction signals that would potentially not translate when applying the risk score to new cohorts. Goodness-of-fit tests may be applied to make sure that the finally selected model fits the data closely. The C-statistic ([Hosmer et al 2013](#)) will be used to compare the goodness of fit of various logistic regression models in terms of how well the predictor(s) discriminate between patients with and without CE-COPD.

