7.5.3. Predicting Severe CE-COPD/Moderate CE-COPD from Multiple Device-Use-Measures

Predictive analysis will be performed by the data analytics group. Additional details may be specified in a separate report. Exploratory predictive analyses will be reported separately.

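### Comparing the six CE-COPD models by C-statistic, with no optimism correction and no common set of patients, tends to favour the accelerometer-subset models

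*Protocol*

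**What the plan says.** Protocol 9.5.2.1 lists six models: albuterol use alone (1), with inspiratory flow (2), with SDI (3), with TDS (4), with flow and SDI (5), and with flow and TDS (6). They are "stepwise selection logistic regression models to select significant predictors in a forward manner", and "The selection of covariates will be performed at the 0.2 level". The candidate pool is wider than the list suggests: "Demographic variables and disease state information collected at study enrollment will also be considered as predictors", and one stated benefit is to "examine the relationship between multiple functional forms for the device-use-measures to determine which forms have predictive power". Interactions get a stricter screen: "Pair-wise interactions will be assessed at the 0.01 significance level". The C-statistic "will be used to compare the goodness of fit of various logistic regression models". The property it is meant to capture is separation at patient level, not day by day: "how well the predictor(s) discriminate between patients with and without CE-COPD".

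Protocol 9.5.1 says SDI comes only from a wrist-device subset and TDS only from an ankle-device subset, 100 patients each. Protocol 9.5.2.2 plans no sensitivity analysis, and 9.6 makes no multiplicity adjustment.

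SAP 7.5.3 states "Predictive analysis will be performed by the data analytics group" and leaves further detail to a possible separate report. SAP 20.4 records that the stepwise analysis was taken out of the SAP. Neither document mentions bootstrap, cross-validation, a hold-out sample, shrinkage or optimism correction.

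**The concern.** A C-statistic computed in the data that built the model is too high. The excess grows as the candidate list lengthens and the number of events falls. Models 3 to 6 have at least one more candidate than model 1 and about a quarter of its events, so their C-statistics are not on the same footing as those of models 1 and 2.

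The study asks which patterns best predict CE-COPD. If full-cohort and subset values are set side by side uncorrected, SDI or TDS may seem to add value when they add none. A later study or device could then carry a sensor that does not help.

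**Working it through.** **The plan's own figure.** Inputs from Protocol 9.1: rates of 1.05 and 1.14 per year (midpoint 1.095), 360 evaluable patients, 12 weeks.
- Expected events: 1.095 × 360 × 12/52 = 90.97, or 91. The Poisson 95% range is 73 to 110 and P(at least 70) = 0.990. All three match the protocol.

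**The same inputs in one accelerometer subset.**
- 90 patients (100 less 10% dropout): 1.095 × 90 × 12/52 = 22.7 events. With all 100: 25.3.
- P(at least one event) = 1 − exp(−1.095 × 12/52) = 0.223. That gives 80 patients with an event among 360, 20 among 90 and 22 among 100.
- The protocol's largest model has 7 covariates: 22.7/7 = 3.2 and 25.3/7 = 3.6 events per variable, against its own rule of 10. The chance of 70 events in a subset is effectively nil.

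**Simulation of apparent C.** Patient-level outcome, forward selection at 0.2 by likelihood-ratio test, 300 replicates per scenario (simulation error about 0.005 on a mean C and 0.03 on a probability). From the documents: sample sizes, event probability, four flow measures, selection level. Assumed: independent normal predictors, 1 or 3 albuterol forms, 0 or 6 baseline candidates. SDI, TDS, flow and baseline variables are pure noise throughout.

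| Scenario | M1 (360) | M2 (360) | M1 refitted (90) | M3 (90) | M5 (90) | M3−M1 | M5−M2 | M3−M1, same 90 |
|---|---|---|---|---|---|---|---|---|
| Albuterol C 0.65, 1 form | 0.650 | 0.661 | 0.639 | 0.651 | 0.695 | +0.001 | +0.034 | +0.012 |
| Albuterol C 0.65, 3 forms | 0.653 | 0.663 | 0.660 | 0.669 | 0.707 | +0.016 | +0.044 | +0.009 |
| As above, 6 baseline candidates | 0.670 | 0.680 | 0.722 | 0.729 | 0.755 | +0.059 | +0.075 | +0.007 |
| All noise, 1 form | 0.510 | 0.550 | 0.523 | 0.545 | 0.612 | +0.035 | +0.062 | +0.022 |
| All noise, 3 forms | 0.535 | 0.567 | 0.571 | 0.588 | 0.652 | +0.053 | +0.085 | +0.017 |

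Models 4 and 6 behave like 3 and 5; the largest model 6 minus model 2 gap with real albuterol is 0.766 − 0.680 = 0.086. In the first three rows model 3 beats model 1 in 56%, 63% and 81% of replicates, and model 5 beats model 2 in 72%, 76% and 88%. Part of this is the wider scatter of C in 90 patients (SD about 0.07 to 0.085 for model 3, against about 0.035 for model 1), not bias alone.

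**Where the gap comes from.** In the third row, subset size contributes 0.722 − 0.670 = 0.052 of the 0.059 and noise SDI 0.007. Where the total gap is small, the two shares are closer or reverse. In new patients, third row, C is 0.628 (M1), 0.585 (M3) and 0.576 (M5), so the apparent order is upside down.

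**Other assumptions.** With correlated albuterol forms and flow values, true albuterol C 0.65 or 0.74 and 0 or 3 baseline candidates, M3−M1 was −0.008 to +0.042 and M5−M2 was +0.02 to +0.06. A further set with albuterol C about 0.65 gave +0.005 to +0.06 and +0.03 to +0.08. With every predictor noise and 6, 12 or 20 candidates, apparent C was 0.56, 0.59, 0.63 in 360 patients and 0.61, 0.69, 0.76 in 90: gaps of 0.05, 0.10 and 0.13.

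**Does the fix work?** Bootstrap correction, third-row scenario, 80 replicates of 30 resamples:
- M1 (360): 0.670 falls to 0.627.
- M1 (90): 0.714 falls to 0.598.
- M3 (90): 0.723 falls to 0.600.
- M5 (90): 0.755 falls to 0.607.

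The mean corrected gain from noise SDI in the same 90 patients is +0.001. Two limits remain. Corrected M1 still differs between 360 and 90 patients (0.627 and 0.598), so correction alone does not make the two sizes comparable. And in 31% of replicates corrected M3 still exceeded refitted M1 by more than 0.01, so a point difference needs an interval.

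**The case against.** The strongest reply is that the criticised text is no longer operative. The SAP introduction gives the SAP precedence, and SAP 20.4 moves the modelling to a report that is not available here. That report may contain a correction. The protocol speaks of comparing models, not ranking them, and does not forbid refitting model 1 in a subset; SAP 3.4 and 3.5 even define the wrist and ankle sets that would allow it. The SAP's one illustrated predictive analysis (7.5.2.3) uses patient-days, so these patient-level values may not carry over. The study is exploratory, and no confirmatory claim rests on the C-statistic.

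Much of this stands. That the C-statistic would be uncorrected is inferred from silence, and the candidate counts are assumptions. But the SAP removes the method without replacing it, so the gap is wider rather than closed. Exploratory status excuses the lack of multiplicity control; it does not make an uneven comparison informative. The protocol itself worries about signals failing in new cohorts, yet applies that caution only to interactions, while main effects enter at 0.2.

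A reader might infer that noise SDI and TDS models will always come out ahead. The documents do not support that: with one real albuterol form and no baseline candidates, models 3 and 4 gain nothing on average (0.651 and 0.644 against 0.650). Nor is 0.13 a fair expectation. It treats albuterol as noise, although Protocol 3.3 reports that reliever use predicted exacerbations, and it assumes 20 independent candidates that appear nowhere in the documents.

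**Conclusion.** The point holds as a tendency. Followed as written, the comparison leans towards the subset models by roughly 0 to 0.06 in C for model 3 against model 1 and 0.02 to 0.08 for model 5 against model 2, when albuterol is truly predictive and SDI or TDS is noise. It is larger with many candidates, up to about 0.13 in the all-noise worst case. Where the gap is large, most of it comes from the smaller subset, not from SDI or TDS.

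This rests on an assumed albuterol C of about 0.65, assumed candidate numbers, a patient-level outcome, and C computed in the fitting data. The documents show an unprotected comparison; they do not show that the analytics group will make it in that form. Confidence is medium, because the study is exploratory and the analytics report cannot be seen.

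**What to change.** In SAP 7.5.3, or in the separate analytics report before the models are run:

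1. Judge SDI only against models 1 and 2 refitted in the same wrist-device patients, and TDS only against models 1 and 2 refitted in the same ankle-device patients.
2. Report bootstrap optimism-corrected C, repeating the whole selection (choice of functional forms and the 0.2 rule) in each resample, with a confidence interval for the difference in C. If patient-days are the unit, resample whole patients.
3. State the candidate list before fitting, since it drives the size of the optimism.

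Both of the first two steps are needed: the refit removes the difference in sample size, and the bootstrap removes most of the remaining optimism.

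The cost is some programming and no new data. Reported C-statistics will be lower, and with about 20 events in a subset the intervals will be wide. That is a fair picture of what 100 patients per device can show.

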9.5.2.2. Sensitivity Analysis

There will be no sensitivity analysis performed in this study.

9.6. Multiple Comparisons and Multiplicity

Because a goal of all of the analyses in this study is to explore a risk-prediction model, no adjustment for multiplicity will be applied.

9.7. Safety Analysis

Safety analyses will be performed on the safety analysis set (Section [9.2.3](#)).

Safety assessments and time points are provided in [Table 1](#).

All adverse events will be coded using the Medical Dictionary for Regulatory Activities. Each patient will be counted only once in each preferred term or System Organ Class category for the analyses of safety. Summaries will be presented for all adverse events (overall and by severity), adverse events determined by the investigator to be related to test IMP (ie, reasonable possibility [Section 7.1.4], defined as related or with missing relationship; overall and by severity), serious adverse events, and adverse events leading to withdrawal from the study. Patient listings of serious adverse events and adverse events leading to withdrawal will be presented.

The use of concomitant medications will be summarized by therapeutic class using descriptive statistics.

For continuous variables, descriptive statistics (number, mean, standard deviation, median, minimum, and maximum) will be provided for actual values and changes from baseline to each time point. For categorical variables, patient counts and percentages will be provided.

Descriptive summaries of serious adverse events, patient withdrawals due to adverse events, and

potentially clinically significant abnormal values (physical examination) based on predefined criteria will be provided as well.

If any patient dies during the study, a listing of deaths will be provided, and all relevant information will be discussed in the patient narrative included in the CSR.

9.8. Tolerability Analysis

Tolerability was not specifically defined.

9.9. Planned Interim Analysis

There will be no formal interim analysis performed in this study.

9.10. Reporting Deviations from the Statistical Analysis Plan

Deviations from the statistical analysis plan, along with the reasons for the deviations, will be described in protocol amendments, the statistical analysis plan, the CSR, or any combination of these, as appropriate, and in accordance with applicable national, local, and regional requirements and regulations.

10. QUALITY CONTROL AND QUALITY ASSURANCE

Refer to [Appendix C](#) for information regarding quality control and quality assurance. This includes information about protocol amendments, deviations and violations, responsibilities of the investigator to study personnel, study monitoring, and audit and inspection.

Details are given in the Study Reference Manual.

11. COMPLIANCE STATEMENT

This study will be conducted in full accordance with the ICH Harmonised Tripartite Guideline for GCP E6 and any applicable national and local laws and regulations (eg, Title 21 CFR [21CFR] Parts 11, 50, 54, 56, 312, and 314, Directive 2001/20/EC of the European Parliament and of the Council on the approximation of the laws, regulations and administrative provisions of the Member States relating to the implementation of GCP in the conduct of clinical trials on medicinal products for human use). Any episode of noncompliance will be documented.

The investigator is responsible for performing the clinical study in accordance with this protocol and the applicable GCP guidelines referenced above for collecting, recording, and reporting the data accurately and properly. Agreement of the investigator to conduct and administer this clinical study in accordance with the protocol will be documented in separate clinical study agreements with the sponsor and other forms as required by national competent authorities in the country where each investigational center is located.

The investigator is responsible for ensuring the privacy, health, and welfare of the patients during and after the clinical study; and must ensure that trained personnel are immediately available in the event of a medical emergency. The investigator and the involved clinical study personnel must be familiar with the background and requirements of the study; and with the properties of the IMPs as described in the IB or prescribing information.

The principal investigator at each investigational center has the overall responsibility for the conduct and administration of the clinical study at that investigational center and for contacts with study management, with the IEC/IRB, and with competent authorities.

See [Appendix D](#) for the ethics expectations of informed consent or assent, competent authorities and IEC and IRB, confidentiality regarding study patients, and requirements for registration of the clinical study.

12. DATA MANAGEMENT AND RECORD KEEPING

See [Appendix H](#) for information regarding data management and record keeping. This includes direct access to source data and documents, data collection, data quality control, and archiving of eCRFs and source documents.

Investigational centers must obtain source documentation of all COPD exacerbations that occur during the treatment period to confirm the accuracy of the information obtained from the patient at monthly phone calls during the 12-week intervention period.

13. FINANCING AND INSURANCE

A separate clinical study agreement, including a study budget, will be signed between each principal investigator and the sponsor (or the CRO designated by the sponsor) before the IMP is delivered.

Patients in this clinical study are insured in accordance with applicable legal provisions. The policy coverage is subject to the full policy terms, conditions, extensions, and exclusions. Excluded from the insurance coverage are *inter alia*, damages to health, and worsening of previous existing disease that would have occurred or continued if the patient had not taken part in the clinical study.

The policy of Clinical Trials Insurance will be provided to the investigational centers by the sponsor.

For covered clinical studies (see 21CFR54), the investigator will provide the sponsor with financial information required to complete FDA 3454 form. Each investigator will notify the sponsor of any relevant changes during the conduct of the study and for 1 year after the study has been completed.

14. PUBLICATION POLICY

See [Appendix I](#) for information regarding the publication policy.

16. SUMMARY OF CHANGES TO PROTOCOL

16.1. Amendment 03 Dated 26 June 2017

The primary reason for this amendment is to clarify the population and endpoint events regarding moderate and severe clinical exacerbation of chronic obstructive pulmonary disease (CE-COPD). Additionally, safety reporting processes were streamlined to facilitate single source reporting through the electronic data capture (EDC) system. This amendment is considered to be substantial (ie, it requires approval by Competent Authority, Independent Ethics Committee [IEC], and/or Institutional Review Board [IRB]) by the sponsor. All text that was removed is denoted by a strikethrough, and all added text is underlined. [Table 1](#) (Study Procedures and Assessments) has been revised to reflect changes described below. Other nonsubstantial changes have been made to the protocol (and protocol synopsis, as appropriate). These changes are unlikely to affect the safety or rights (physical or mental integrity) of the patients in this clinical study or the scientific value of the clinical study.

Changes to the Protocol

Original text with changes shown	New wording	Reason/justification for change
CLINICAL STUDY PROTOCOL SYNOPSIS (Other section affected by these changes: Global)		
Number of Patients Planned (Total): Approximately 500 patients will be screened to achieve 400 enrolled patients. A subset of patients (n=100) who agree to participate at specific sites investigational centers will wear an accelerometer on the wrist to measure sleep disruption index (SDI). A second subset of patients (n=100) who agree to participate at specific sites investigational centers will wear an accelerometer on the ankle to measure total daily steps (TDS).	Number of Patients Planned (Total): Approximately 500 patients will be screened to achieve 400 enrolled patients. A subset of patients (n=100) who agree to participate at specific investigational centers will wear an accelerometer on the wrist to measure sleep disruption index (SDI). A second subset of patients (n=100) who agree to participate at specific investigational centers will wear an accelerometer on the ankle to measure total daily steps (TDS).	The word “site” was replaced by “investigational center” throughout to maintain consistency in terminology.
CLINICAL STUDY PROTOCOL SYNOPSIS (Other section affected by these changes: Section 2.1, Section 9.4)		
Study Population: The cohort will consist of patients 40 years of age or older with “severe” moderate or severe clinical exacerbation of COPD (CE-COPD; defined in Section 6.1.1 of the protocol) in the past 12 months.	Study Population: The cohort will consist of patients 40 years of age or older with moderate or severe clinical exacerbation of COPD (CE-COPD; defined in Section 6.1.1 of the protocol) in the past 12 months.	This change was made to specify that CE-COPD can include moderate as well as severe exacerbation.

CLINICAL STUDY PROTOCOL SYNOPSIS (Other sections affected by these changes: Section 1.1, Section 1.3, Section 2, Section 3.1, Section 6, Section 6.1.2, Section 9.1, Section 9.5.1)**Objectives and Endpoints:**

The endpoints of the trial are the primary outcome measure (ie, CE-COPD/~~severe CE COPD~~) and the primary outcome predictor (ie, albuterol use) alone or in combination with secondary predictors (ie, other study data). These predictors of CE-COPD/~~severe CE COPD~~ will be modeled to determine which patterns best predict the subsequent development of CE-COPD/~~severe CE COPD~~.

For albuterol use, parameters of interest will include (1) the total number of inhalations in the days preceding the peak of a ~~severe~~ CE-COPD, (2) the number of days prior to the peak of a ~~severe~~ CE-COPD when albuterol use increased, and (3) the number of albuterol uses in the 24 hours preceding a ~~severe~~ CE-COPD. Therefore, endpoints are not designated as either primary or secondary.

In addition to albuterol use, inspiratory flow values (maximal inhalational flow [MIF], inhalational volume, inhalation duration, and time to MIF), SDI, TDS, and baseline information regarding disease state and demographics will be studied. These data will be analyzed using both a univariate and multivariate approach, to determine which patterns best predict the subsequent development of a CE-COPD ~~or~~ ~~severe CE COPD~~.

Objectives and Endpoints:

The endpoints of the trial are the primary outcome measure (ie, CE-COPD) and the primary outcome predictor (ie, albuterol use) alone or in combination with secondary predictors (ie, other study data). These predictors of CE-COPD will be modeled to determine which patterns best predict the subsequent development of CE-COPD.

For albuterol use, parameters of interest will include (1) the total number of inhalations in the days preceding the peak of a CE-COPD, (2) the number of days prior to the peak of a CE-COPD when albuterol use increased, and (3) the number of albuterol uses in the 24 hours preceding a CE-COPD. Therefore, endpoints are not designated as either primary or secondary.

In addition to albuterol use, inspiratory flow values (maximal inhalational flow [MIF], inhalational volume, inhalation duration, and time to MIF), SDI, TDS, and baseline information regarding disease state and demographics will be studied. These data will be analyzed using both a univariate and multivariate approach, to determine which patterns best predict the subsequent development of a CE-COPD

This change was made to allow for inclusion of all CE-COPD events, not just severe events.

CLINICAL STUDY PROTOCOL SYNOPSIS (Other sections affected by these changes: Section 3.1, Section 3.5 [Table 1, footnote e], Section 5.1, Section 5.2.3)

General Design: Patients will be instructed to return all inhalers to the ~~site~~investigational center at the last study visit, ~~at the CE COPD visit, or earlier, including at the early termination visit, as well as at any other point if there is a problem with the inhaler.~~

General Design: Patients will be instructed to return all inhalers to the investigational center at the last study visit or earlier, including at the early termination visit, as well as at any other point if there is a problem with the inhaler.

This parameter was added to clarify when the patients should return their inhaler to the investigational center.

CLINICAL STUDY PROTOCOL SYNOPSIS (Other sections affected by these changes: Section 1.3, Section 5.8)		
Method of Randomization and Blinding: This is a nonrandomized open-label study and there will be no blinding study. All patients will use the one Test IMP, the ABS eMDPI. Blinding is not applicable.	Method of Randomization and Blinding: This is a nonrandomized study. All patients will use the one Test IMP, the ABS eMDPI. Blinding is not applicable.	The term “open-label” was removed from all non-title related text because the study does not involve randomization.
CLINICAL STUDY PROTOCOL SYNOPSIS (Other sections affected by these changes: Section 3.1)		
Duration of Patient Participation and Maximal Exposure to IMP: The total duration of patient participation in the study is planned to be up to 14 weeks (2 weeks a screening period of up to 2 weeks and a 12-week intervention period).	Duration of Patient Participation and Maximal Exposure to IMP: The total duration of patient participation in the study is planned to be up to 14 weeks (a screening period of up to 2 weeks and a 12-week intervention period).	This change was made to indicate that patient participation in the study includes a screening period that is 2 weeks in duration or less.
CLINICAL STUDY PROTOCOL SYNOPSIS (Other sections affected by these changes: Section 4.1)		
Inclusion Criteria: Patients may be enrolled in the study only if they meet all of the following criteria: a. The patient is male or female, 40 years of age or older, with a physician diagnosis of COPD. The diagnosis should include a history within the past 3 months of forced expiratory volume in 1 second (FEV ₁)/forced vital capacity <70% predicted and FEV ₁ <80% predicted documented in the patient's chart . g. The patient is willing to discontinue all other rescue or maintenance SABA or short-acting anti-muscarinic agents and replace them with the study-provided ABS eMDPI for the duration of the trial. h. Women of childbearing potential (not surgically sterile or ≥ 2 years postmenopausal) must have exclusively same-sex partners or use a highly effective method or acceptable method of birth control and must agree to continue the use of this method for the duration of the study and for 30 days after discontinuation of the IMP. Highly effective methods of birth control are defined as those, alone or in combination, that result in a low failure rate (ie, <1% per year) when used consistently and correctly. Highly effective methods of birth control in this study include combined (estrogen- and progestogen-containing) or progestogen-only	Inclusion Criteria: Patients may be enrolled in the study only if they meet all of the following criteria: a. The patient is male or female, 40 years of age or older, with a physician diagnosis of COPD. The diagnosis should include a history of forced expiratory volume in 1 second (FEV ₁)/forced vital capacity <70% predicted and FEV ₁ <80% predicted documented in the patient's chart. g. The patient is willing to discontinue all other rescue or maintenance SABA or short-acting anti-muscarinic agents and replace them with the study-provided ABS eMDPI for the duration of the trial. h. Women of childbearing potential (not surgically sterile or ≥ 2 years postmenopausal) must have exclusively same-sex partners or use a highly effective or acceptable method of birth control and must agree to continue the use of this method for the duration of the study and for 30 days after discontinuation of the IMP. Highly effective methods of birth control are defined as those, alone or in combination, that result in a low failure rate (ie, <1% per year) when used consistently and correctly. Highly effective methods of birth control in this study include combined (estrogen- and	Clarification added around patient's medical history. Verbiage added around acceptable method of birth control.


hormonal contraception associated with inhibition of ovulation, intrauterine device, intrauterine hormone-releasing system, bilateral tubal occlusion, vasectomized partner, and sexual abstinence. Acceptable birth control methods that result in a failure rate of more than 1% per year include: progestogen-only oral hormonal contraception, for which the inhibition of ovulation is not the primary mode of action; male or female condom with or without spermicide; and cap, diaphragm, or sponge with spermicide. The combination of male condom with either cap, diaphragm, or sponge with spermicide (double barrier methods) are also considered acceptable, but not highly effective, methods of birth control.
	
progestogen-containing) or progestogen-only hormonal contraception associated with inhibition of ovulation, intrauterine device, intrauterine hormone-releasing system, bilateral tubal occlusion, vasectomized partner, and sexual abstinence. Acceptable birth control methods that result in a failure rate of more than 1% per year include: progestogen-only oral hormonal contraception, for which the inhibition of ovulation is not the primary mode of action; male or female condom with or without spermicide; and cap, diaphragm, or sponge with spermicide. The combination of male condom with either cap, diaphragm, or sponge with spermicide (double barrier methods) are also considered acceptable, but not highly effective, methods of birth control.
	
--	---	--

CLINICAL STUDY PROTOCOL SYNOPSIS (Other sections affected by these changes: Section 9.1)		

Statistical Considerations:
 
Sample Size Rationale:
 
Based on previous studies of an exacerbation-prone COPD cohort (Dransfield et al 2013, Vogelmeier et al 2011, Wedzicha et al 2013, Wedzicha et al 2016), it is expected that 91 (range, 73 to 110) CE-COPD events will occur over the 12-week evaluation period in this study based on reported CE-COPD exacerbation rates of 1.05 and 1.14 events per year. Furthermore, it is expected that 14% (14) of total exacerbations will be severe.
 
This sample size (ie, n=400 patients, 73 to 110 CE-COPD events) is considered adequate for the fulfillment of the study objectives using univariate and multivariate analyses to evaluate the relationship of the pattern of albuterol use, inspiratory flow, SDI, and TDS data associated with the subsequent development of a CE-COPD event. Per a previous study (Jenkins et al 2013), a statistically significant relationship was established between daily SABA usage and subsequent CE-COPD.
 
In the present study, approximately 73 to 110 CE-COPD events are desired because the model's fitting of the current study involves the analysis of multiple predictors as described in more detail below. Because the largest model considered has 7 covariates, it is desirable to have at least 70 events. The probability to observe at least 70 CE-COPD events is higher than 0.99.
	
Statistical Considerations:
 
Sample Size Rationale:
 
Based on previous studies of an exacerbation-prone COPD cohort (Dransfield et al 2013, Vogelmeier et al 2011, Wedzicha et al 2013, Wedzicha et al 2016), it is expected that 91 (range, 73 to 110) CE-COPD events will occur over the 12-week evaluation period in this study based on reported CE-COPD exacerbation rates of 1.05 and 1.14 events per year. Furthermore, it is expected that 14% (14) of total exacerbations will be severe.
 
This sample size (ie, n=400 patients, 73 to 110 CE-COPD events) is considered adequate for the fulfillment of the study objectives to evaluate the relationship of albuterol use, inspiratory flow, SDI, and TDS data associated with a subsequent CE-COPD event. Per a previous study (Jenkins et al 2013), a statistically significant relationship was established between daily SABA usage and subsequent CE-COPD.
 
In the present study, approximately 73 to 110 CE-COPD events are desired because the model's fitting of the current study involves the analysis of multiple predictors as described in more detail below. Because the largest model considered has 7 covariates, it is desirable to have at least 70 events. The probability to observe at least 70 CE-COPD events is higher than 0.99.
	
The range of values in the prior sample size estimate was based on the mean results reported in the literature. The updated sample size estimate correctly incorporates sample variability into the range likely in this study.

CLINICAL STUDY PROTOCOL SYNOPSIS (Other sections affected by these changes: Section 9.5.2.1)		

Analysis of Endpoints: The relationship between albuterol usage and CE-COPD will be analyzed as follows, without controlling for multiplicity.
 
The multiple device-use-measures will be used as predictors of CE-COPD in the following stepwise selection logistic regression models to select significant predictors in a forward manner:
	
Analysis of Endpoints: The relationship between albuterol usage and CE-COPD will be analyzed as follows, without controlling for multiplicity.
 
The multiple device-use-measures will be used as predictors of CE-COPD in the following stepwise selection logistic regression models to select significant predictors in a forward manner:
	
Text was added to clarify the multiple comparisons within the analyses listed below, as well as the addition of a rule for covariate selection.
 
Text was deleted because the modeling of secondary analyses is not part of the hypothesis-testing procedure.

